4 TREATMENTS

4.1 Identification of Investigational Product

4.1.1 Test Drug(s)

ELIGARD[®] 22.5 mg is intended to be administered subcutaneously and provides continuous release of leuprolide acetate over a 3-month treatment period. ELIGARD[®] is a long-acting depot formulation that uses Atrigel[®] delivery system (a biodegradable polymer matrix) to deliver leuprolide acetate at a controlled rate over a therapeutic period.

Subcutaneous administration of ELIGARD[®] is as per the label and approved indications of ELIGARD[®]. (*Refer to the current local ELIGARD prescribing information.*)

ELIGARD[®] will be prescribed by treating physician according to local prescribing information. ELIGARD[®] will be provided in this study. ELIGARD[®] should be stored in a refrigerator (2-8°C), and will be stable for 24 months from the date of manufacturing when stored at 2-8°C.

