5 TREATMENTS AND EVALUATION

5.1 Dosing and Administration of Study Drug(s) and Other Medication(s)

5.1.1 Dose/Dose Regimen and Administration Period

ELIGARD® 22.5mg is administered subcutaneously and provides continuous release of leuprolide acetate over a 3-month treatment duration. ELIGARD® is a long-acting depot formulation that uses Atrigel® delivery system (a biodegradable polymer matrix) to deliver leuprolide acetate at a controlled rate over a therapeutic period.

Subcutaneous administration of ELIGARD® 22.5mg is as per the label and approved indications of ELIGARD®. Refer to the current local ELIGARD® prescribing information.

ELIGARD® will be prescribed by treating physician according to local prescribing information. ELIGARD® will be provided by the sponsor during the conduct of this study.

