5.6.1 Definition of Adverse Events (AEs)

An AE is defined as any untoward medical occurrence in a patient administered a study drug or has undergone study procedures and which does not necessarily have a causal relationship with this treatment. An AE can therefore be any unintended sign (including an abnormal laboratory finding), symptom, or disease temporally associated with the use of a medicinal (investigational) product, whether or not related to the medicinal (investigational) product.

An abnormality identified during a medical test (e.g., laboratory parameter, vital sign, electrocardiogram [ECG] data, physical exam) should be defined as an AE only if the abnormality meets 1 of the following criteria:

- Induces clinical signs or symptoms
- Requires active intervention
- Requires interruption or discontinuation of study medication
- The abnormality or investigational value is clinically significant in the opinion of the investigator.

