For patients who discontinue ELIGARD[®] treatment, AE monitoring should be continued for a period of 3 months from the date of last administration of ELIGARD[®], provided consent is not withdrawn. AE documentation and SAEs reporting should be continued during this period of time. SAEs that are considered to be related to ELIGARD[®] occurring after the end of the observation period or after end of the follow-up period should be reported according to local law/guidelines within the spontaneous reporting system.

Safety Observations

The investigator should take all appropriate measures to ensure the safety of the patients. The outcome of all reported SAEs (e.g., resolution, death) will be followed up and documented. Reporting to the relevant Regulatory Authorities according to national regulations will be done by the Sponsor.

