5.6.6 Follow-up of Adverse Events

All AEs occurring during or after the patient has discontinued the study are to be followed-up until resolved or judged to be no longer clinically significant, or until they become chronic to the extent that they can be fully characterized.

If during AE follow-up, the AE progresses to an "SAE", or if a patient experiences a new SAE, the investigator must immediately report the information to the Sponsor.

Please refer to **Appendix 12.3 Liver Safety Monitoring and Assessment** for detailed instructions on Drug Induced Liver Injury (DILI).

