6 DISCONTINUATION

6.1 Discontinuation of Individual Patients

A discontinuation is a patient who enrolled in the study and for whom study treatment is permanently discontinued prematurely for any reason.

A patient is free to withdraw from the study for any reason, at any time, without reason for doing so and without penalty or prejudice.

A patient will be discontinued from the study in the case of:

1. Withdrawal of consent - patient decision to withdraw from further participation in the study
2. Patient safety is at risk (at the discretion of the treating physician)
3. Patient develops CRPC as determined by European Association of Urology (EAU) Prostate Cancer Guidelines 2016
4. Patient is lost to follow-up
5. Patient death during the study
6. Patient misses consecutive visit periods (window \pm 14 days) during the study
7. Patient who is less than 80% compliant with the dosage regimen for any 2 consecutive visit periods (window \pm 14 days) during the study.
8. Site terminated by the Sponsor
9. Study terminated by the Sponsor
10. Cessation of treatment with ELIGARD[®] (at the discretion of the treating physician). The reasons for stopping treatment will be noted (e.g., PSA progression, radiographic progression, clinical progression, AE, drug administration issues, other).
11. Patient takes prohibited medications as described in Section 5.1.6 and Section 12.2

For patients that discontinue from the study, the reason for discontinuation should be recorded in the eCRF. Patients that discontinue will have an Early Withdrawal visit 3 months after the last administration of ELIGARD[®] for safety assessment. At the end of a patient's involvement in this study, the Investigator must ensure that all outstanding data entry is entered in the eCRF unless the patient withdrew consent for their data to be used.

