12.3 Liver Safety Monitoring and Assessment

Any patient enrolled in a clinical study with active drug therapy and reveals an increase of serum aminotransferases (AT) to $> 3 \times$ upper limits of normal (ULN) (to $> 5 \times$ ULN in patients with liver metastases), or bilirubin $> 2 \times$ ULN, should undergo detailed testing for liver enzymes (including at least ALT, AST, ALP, and TBL). Testing should be repeated within 48-72 hours of notification of the test results. Patients should be asked if they have any symptoms suggestive of hepatobiliary dysfunction.

Definition of Liver Abnormalities

Confirmed abnormalities will be characterized as moderate and severe where ULN:

	ALT or AST		Total Bilirubin
Moderate	$> 3 \times$ ULN (in patients without liver metastases), $> 5 \times$ ULN (in patients with liver metastases)	or	$> 2 \times$ ULN
Severe*	$> 3 \times$ ULN	and	$> 2 \times$ ULN

In addition, the patient should be considered to have severe hepatic abnormalities for any of the following:

ALT or AST $> 8 \times$ ULN

ALT or AST $> 5 \times$ ULN for more than 2 weeks (in the absence of liver metastases)

ALT or AST $> 3 \times$ ULN and INR > 1.5 (If international normalized ratio [INR] testing is applicable/evaluated).

ALT or AST $> 3 \times$ ULN with the appearance of fatigue, nausea, vomiting, right upper quadrant pain or tenderness, fever, rash and/or eosinophilia ($>5\%$).

The investigator may determine that abnormal liver function results, other than as described above, may qualify as moderate or severe abnormalities and require additional monitoring and follow-up.

Follow-up Procedures

Confirmed moderate and severe abnormalities in hepatic functions should be thoroughly characterized by obtaining appropriate expert consultations, detailed pertinent history, physical examination, and laboratory tests. The site should complete the Liver Abnormality Case Report Form (LA-CRF) that has been developed globally and can be activated for any study or appropriate document. Patients with confirmed abnormal LFT should be followed as described below.

Confirmed moderately abnormal LFTs should be repeated 2-3 times weekly then weekly or less if abnormalities stabilize or the study drug has been discontinued and the patient is asymptomatic.

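### For a confirmed moderate liver abnormality, Appendix 12.3 lets testing thin out in an asymptomatic patient once study drug is stopped, even with unstable values, although the last depot may still be releasing

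*Protocol*

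**What the plan says.** Protocol Appendix 12.3 (Follow-up Procedures) sets the retest schedule for confirmed moderate abnormalities: they should be "repeated 2-3 times weekly then weekly or less if abnormalities stabilize or the study drug has been discontinued and the patient is asymptomatic". It gives no minimum frequency for the reduced phase.

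Section 4.1.1 says that the 22.5 mg product "provides continuous release of leuprolide acetate over a 3-month treatment period", and Section 5.1.1 likewise describes "continuous release of leuprolide acetate over a 3-month treatment duration".

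Elsewhere the protocol allows for exposure that outlasts the decision to stop. Section 5.6.5 says that after discontinuation "AE monitoring should be continued for a period of 3 months from the date of last administration", and Section 6.1 adds that "Patients that discontinue will have an Early Withdrawal visit 3 months after the last administration".

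Two general rules also bear on the point. Under Section 5.6.1 a test abnormality counts as an adverse event if, among other criteria, it "Requires interruption or discontinuation of study medication". Section 5.6.6 states that "All AEs occurring during or after the patient has discontinued the study are to be followed-up until resolved", or until they are no longer clinically significant or are chronic and fully characterised.

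**The concern.** The retest rule puts stopping the drug on a par with stable enzymes as a reason to test less. That is sensible where stopping ends exposure within days. Here, withholding the next injection does nothing about the one already given. A patient with rising transaminases who is stopped one month into a dosing interval has about two months of labelled release ahead, and the appendix allows sparser testing from the moment of stopping.

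What is at stake is how soon further worsening is seen in a patient without symptoms. Several criteria for a severe abnormality in Appendix 12.3 are purely laboratory findings, so they are recognised only if blood is drawn. Other liver tests are no backstop: Section 5.5.3 collects them only when they are done in routine practice.

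**Working it through.** **1. Does the clause allow it?** Take an asymptomatic patient with a confirmed moderate abnormality, values not stable, drug stopped.

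- Grouping A, stable OR (stopped AND asymptomatic): false OR (true AND true) = true.
- Grouping B, (stable OR stopped) AND asymptomatic: (false OR true) AND true = true.

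Reduced testing is allowed on both groupings, so the ambiguity of the sentence does not matter here.

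**2. How much release is left at the stop?** Inputs: a 3-month release period (Sections 4.1.1 and 5.1.1) and a 30-day month (Section V, notes to the flow chart), so 3 x 30 = 90 days. With t days since the last injection, labelled release left = 90 - t.

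- Stop at day 30: 90 - 30 = 60 days.
- Stop at day 60: 90 - 60 = 30 days.
- Dose withheld at a visit on day 90: about 0 days.
- Dose withheld at the early edge of the 14-day visit window (day 76): 90 - 76 = 14 days.

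Section 1.2 reports near-complete release by Day 106 in non-clinical work, 106 - 90 = 16 days beyond the labelled period. That would lengthen each figure somewhat if it carried over to patients, which the protocol does not say. The concern therefore bears mainly on stops between scheduled injections. Section 6.1, item 10, permits these at the physician's discretion.

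**3. How much later could worsening be seen?** Assume equally spaced tests, with the weekly test falling on one of the days of the denser schedule.

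| Schedule | Gap between tests | Added delay under weekly testing, at most |
|---|---|---|
| 3 per week | 7/3 = 2.3 days | 7 - 2.3 = 4.7 days |
| 2 per week | 7/2 = 3.5 days | 7 - 3.5 = 3.5 days |
| Weekly | 7 days | reference |
| Sparser than weekly | not stated | no limit can be given |

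These delays apply to criteria that a single blood draw can show: ALT or AST above 8 x ULN, or ALT or AST above 3 x ULN together with bilirubin above 2 x ULN.

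**4. Do other rules set a testing frequency?** Sections 5.6.1, 5.6.5, 5.6.6 and 6.1 require that events be recorded, monitored for 3 months and followed to resolution. None says how often liver tests are to be done. The rest of Appendix 12.3 requires work-up and allows investigator judgement, but it also sets no frequency for a patient who has stopped.

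**The case against.** The case against is substantial, and part of it stands.

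- **Little follows from earlier detection.** In a patient already off drug, reaching severe leads to possible SAE reporting, informing the sponsor and work-up. The appendix sets no denser testing for severe abnormalities, and the protocol describes no way to end depot release. This stands, and it is the main reason why the point ranks low.
- **Safeguards exist.** The wording implies an initial phase of 2 to 3 tests a week, the reduced schedule is permissive, and confirmed moderate cases already call for expert consultation and laboratory work-up. This stands too. A reader might infer that a patient who stops is left without hepatic follow-up; the adverse event rules in Sections 5.6.1, 5.6.5 and 5.6.6 rule that out. What is missing is only a liver-test frequency tied to stability.
- **The criterion "for more than 2 weeks (in the absence of liver metastases").** A reader might infer a delay of a week or more in recognising this route to severe. The documents do not support that as a cost of the discontinuation clause. A patient steady at, say, 6 x ULN counts as stable and could be tested sparsely under any wording that keys on stability. The day of recognition also turns on whether a draw lands on day 14 or just after it. No delay is claimed for this criterion.
- **Conflict within the appendix.** Appendix 12.3 also tells investigators to stop drug when a patient with moderate or severe liver tests cannot be monitored closely. A flat demand for 2 to 3 tests a week after stopping would ask for what has just been found impossible. This is right, and the proposed wording has to allow for it.
- **Rarity.** Sections 1.2 and 1.3 name no hepatic reaction among the key safety findings, and the protocol gives no rate of liver abnormalities or of mid-interval stops. The number affected is unknown and probably low.

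None of this removes the basic mismatch: the rule treats stopping as a substitute for stability, for a product in which stopping does not end exposure.

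**Conclusion.** The point holds as a small safety-monitoring improvement. On any reading, the rule lets testing thin out in an asymptomatic patient with unstable moderate abnormalities solely because drug was stopped, while the last depot may still be releasing. The added delay in seeing a single-draw laboratory criterion is at most about 3.5 to 4.7 days under weekly testing, and unbounded on paper if testing is sparser.

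This rests on equally spaced tests, on the labelled 3-month release period, and on a stop that falls between injections; at an on-time scheduled visit the labelled release left is about 0 days. A reader might infer that every patient who discontinues faces three months of under-monitored exposure. The documents do not support that, since the gap needs a moderate abnormality, no symptoms, unstable values and, mainly, a mid-interval stop all at once. Sample size, the primary endpoint and its analysis are not affected. Lowest severity, worth making because it is cheap.

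**What to change.** Replace the relaxation clause in Appendix 12.3 (Follow-up Procedures) with wording along these lines:

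> … then weekly or less once abnormalities are stable or resolving and the patient is asymptomatic. Discontinuing study drug does not by itself allow reduced testing while the last depot may still be releasing (about 3 months after the last injection), except where closer testing is not feasible; in that case test as often as is feasible and document the reason.

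The exception keeps the sentence consistent with the appendix's instruction to stop drug when close monitoring is not possible.

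Cost: one sentence, plus 2 - 1 = 1 to 3 - 1 = 2 extra local liver tests a week, compared with weekly testing, while values remain unstable. If they settle within 2 weeks, that is 2 x 1 = 2 to 2 x 2 = 4 extra tests per affected patient.

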12.4 Common Serious Adverse Events

The following is a list of serious adverse events that the Sponsor considers to be associated with the disease state being studied. **The list does NOT change your reporting obligations or prevent the need to report an adverse event meeting the definition of an SAE as detailed in Section 5.6.2 Definition of Serious Adverse Event (SAE).** The purpose of this list is to alert you that some events reported as SAEs may not require expedited reporting to the regulatory authorities based on the classification of “common serious adverse events”. You are required to follow the requirements detailed in **Section 5.6.5 Reporting of Serious Adverse Events (SAE).**

Common Serious Adverse Events due to prostate cancer include:

- Urinary flow obstruction
- Hematuria
- Spinal cord compression/ Paraplegia
- Pleural effusion
- Bone fractures

12.5 EQ5D-5L Questionnaire

12.6 EORTC QLQ-PR25 Questionnaire

12.7 Protocol Amendment Summary Document

Protocol Amendment Summary Document
ISN/Protocol 7015-MA-3072
Substantial Amendment Version 2.0
18 April 2018

I. The purpose of this amendment is:

Substantial Changes
1. Update Protocol Title
DESCRIPTION OF CHANGE: Remove the description of efficacy and quality of life from the protocol title.
RATIONALE: The protocol is revised to reflect the primary objective of this study for establishing the safety profile of ELIGARD® in ethnic Asian prostate cancer patients.
2. Update Sample Size , Study Period and Center Numbers for the Study
DESCRIPTION OF CHANGE: The sample size for this study is revised to approximately 107 enrolled prostate cancer patients, with 96 completed patients. The number of participating centers in the study is revised to 20 centers. The planned total duration of the study is revised to 30 months from the date of first patient enrollment until 3 months after the last dose of ELIGARD® administration. The enrollment period is revised to 12 months.
RATIONALE: The sample size is revised based on the rationale that more than 90% of subjects will have Testosterone level of 20-50mg/dL. The original sample (N=345) will not lead to effective analysis in the study cohorts based on Testosterone levels and hence no added substantial impact with reduction in sample size. In addition, this study is not a registration study and multiple global data from LHRH analogues is available that a wider confidence interval should not have a meaningful risk. The study timeline is shortened considering 107 patients rather than 345 patients will be enrolled. The number of 20 participating sites is based on the sample size of 345 patients. However, because RA approval and EC submission for all 20 countries have been done, it has been decided to keep all 20 sites.

3. Update Table 1 Schedule of Assessments
DESCRIPTION OF CHANGE:
Add language to clarify the choices available in eCRF for the most important factors for selection of treatment, including rising PSA after definitive treatment, optimal testosterone control, quality of life, convenience of 3-monthly formulation, and other.
Add language in the footnote f to clarify the Visual Analogue Scale (VAS) will only be collected if done in routine clinical practice.
RATIONALE:
The reasons for selection of treatment with ELIGARD® 22.5mg will be collected at the baseline visit. Examples for potential factors, such as rising PSA after definitive treatment, optimal testosterone control, quality of life and convenience of use, are added as a guidance in the assessment schedule table.
4. Update Concomitant Treatment Definition
DESCRIPTION OF CHANGE:
Include language to clarify the appropriate anti-androgen should be considered beginning at least 3 days to 4 weeks prior to ELIGARD® injection and continuing for the first 2 to 3 weeks of treatment.
RATIONALE:
The revision is to keep consistency with the following statement in Section V Flow Chart and Schedule of Assessment. Anti-androgen for at least 3 days to 4 weeks prior to the first ELIGARD® injection and continuing for the first 2 to 3 weeks of treatment should be considered.
5. Add One Additional Definition For Discontinuation
DESCRIPTION OF CHANGE:
One additional condition for discontinuation is added to define patients will be discontinued from the study in the case of patient taking prohibited medications as described in protocol Section 5.1.6 and Section 12.2.
RATIONALE:
The drugs prohibited to be used throughout the study are described in protocol Section 5.1.6 and Section 12.2. Individual patients who are enrolled in the study and take prohibited medications during the study course should be discontinued prematurely from the study.
6. Update Selection of Study Population and Inclusion Criteria

DESCRIPTION OF CHANGE:
Include wording of “and” to include patients with locally advanced prostate cancer with biochemical relapse following radical prostatectomy and radiotherapy.
Include wording of “OR” to make inclusion criteria #4 and #5 as one criterion.
RATIONALE:
To include the patients with locally advanced prostate cancer with biochemical relapse following radical prostatectomy only, radiotherapy only, both radical prostatectomy and radiotherapy.
The criteria of “Locally advanced prostate cancer with biochemical relapse following radical prostatectomy and/or radiotherapy” and “Hormonal treatment-naive advanced or metastatic prostate cancer patient who has not received chemotherapy and has no plans to undergo treatment with chemotherapy at study entry” are not both possible to be met in one particular patient.
7. Update Interim Analyses Cut-Off Time and Condition
DESCRIPTION OF CHANGE:
The schedule of the interim analysis is revised to be conducted when 50 of the patients complete 1 year of follow-up after the first patient is enrolled.
RATIONALE:
To specify the estimated number of patients to be included in the interim report, and to revise the criteria that patients to be analyzed will be those who complete 1 year of follow up instead of those who complete treatment, since treatment may stop for various reasons during the study.
8. Update background information for ELIGARD® Risk Management Plans (RMP)
DESCRIPTION OF CHANGE:
Add “QT prolongation” in Section 1.2 Clinical data to include major updates of ELIGARD® RMP.
RATIONALE:
The QT prolongation was added because the ELIGARD RMP was updated to version 7.0 and submitted at the end of Oct 2017 to the Health Authorities. The summary of the major updates is listed below: 1. QT prolongation was added as one of the new important identified risks.

2. The other safety concerns remained the same, including important identified risks renamed as “Transient testosterone flare”, “Diabetes and hyperglycemia” & “Convulsions” which has been covered in Section 1.2 of the protocol.

Non-Substantial Changes
1. Update Contact Details of Key Sponsor’s Personnel
DESCRIPTION OF CHANGE:
Include minor administrative-type changes.
RATIONALE:
To provide clarifications to the protocol and to ensure complete understanding of study procedures.
2. Update Timeline of Study Period
DESCRIPTION OF CHANGE:
Update timeline for each milestone of the study, including start and end of data collection, final report of study results and publication.
RATIONALE:
The study timeline is updated due to the changes of sample size from 345 to 107 enrolled patients.
3. Update Flow Chart and Schedule of Assessment
DESCRIPTION OF CHANGE:
Add language in the footnote clarifying the definition of “one month=30 days.”
RATIONALE:
To provide clarifications to the protocol and to ensure complete understanding of study population

4. Minor Administrative-type Changes
DESCRIPTION OF CHANGE:
Include minor administrative-type changes, e.g., document version, format, typo, consistency, citation and reference style throughout the protocol following STL1015
RATIONALE:
To provide clarifications and writing style consistency to the protocol and to ensure complete understanding of study population
5. Update Analysis of Secondary Endpoints
DESCRIPTION OF CHANGE:
Update language to specify the measurement of time to PSA progression is calculated from date of first administration of ELIGARD® 22.5 mg to PSA progression.
RATIONALE:
Include format type changes to specify the definition for time to PSA progression.

II. Amendment Summary of Changes:

Front Page, IV Synopsis Title of Study
WAS:
A Phase IV Interventional Safety, Efficacy and Quality of Life Study of ELIGARD® in Prostate Cancer Patients in Asia (ELIGANT)
IS AMENDED TO:
A Phase IV Interventional Safety, Efficacy and Quality of Life Study of ELIGARD® in Prostate Cancer Patients in Asia (ELIGANT)

II. Contact Details of Key Sponsor's Personnel
WAS:
Sponsor's personnel: 24h-Contact for Serious Adverse Events (SAEs): See Section 5.6.5 Quintiles Lifecycle Safety Email: [contact] [contact]
Medical Monitor: PPD [Redacted] [Redacted] [Redacted]
Clinical Research Contacts: PPD [Redacted] [Redacted] [Redacted]
PPD [Redacted] [Redacted] [Redacted]
IS AMENDED TO:
Sponsor's personnel: 24h-Contact for Serious Adverse Events (SAEs): See Section 5.6.5 Quintiles IQVIA Lifecycle Safety Email: [contact] QLS [contact]

[contact]
Medical Monitor:
PPD
PPD
Clinical Research Contacts:
PPD
PPD
PPD

IV Synopsis
Planned Study Period
WAS:
From Q1 2017 to Q1 2020 Start of data collection: Q1 2017 End of data collection: Q1 2020 Final report of study results: Q4 2020 Publication: Q4 2021
IS AMENDED TO:
From Q1 2017 Q2 2017 to Q1 2020

Start of data collection: Q1 2017 Q2 2017 End of data collection: Q1 2020 Final report of study results: Q4 2020 Q3 2020 Publication: Q4 2021 Q3 2021

V Flow Chart and Schedule of Assessments

Flow Chart: Footnote

ADDED:

One month=30 days

V Flow Chart and Schedule of Assessments

Table 1 Schedule of Assessments
--

WAS:

Most important factors for selection of treatment

IS AMENDED TO:

Most important factors for selection of treatment (Rising PSA after definitive treatment, optimal testosterone control, quality of life, convenience of 3 monthly formulation, other).

V Flow Chart and Schedule of Assessments

Table 1 Schedule of Assessments – Footnote f.
--

WAS:

f. Prostate cancer status - stage of prostate cancer, bone metastasis, soft tissue disease, visceral disease, pain (using Visual Analogue Scale (VAS) 0-10), ECOG status
--

IS AMENDED TO:

f. Prostate cancer status - stage of prostate cancer, bone metastasis, soft tissue disease, visceral disease, pain (using Visual Analogue Scale [VAS] 0-10 which will only be collected if done in routine clinical practice), ECOG status

1. Introduction

